
Efficacy in diffuse large B-cell lymphoma

In Study GEN415/OMB111776, 81 subjects with CD20+ relapsed DLBCL ineligible for autologous stem cell transplantation or DLBCL which had relapsed or progressed after autologous stem cell transplantation were treated with ofatumumab 300 mg for the first IV infusion, followed by seven weekly infusions of ofatumumab 1000 mg. The ORR was 11% (3 CR and 6 PR). In Study OMB110927, 61 subjects with relapsed or refractory CD20+ aggressive B-cell NHL who were transplant eligible were treated with ofatumumab + ICE (n=35) or ofatumumab + DHAP (n=26). Chemotherapy was dosed every 21 days for 3 cycles, while ofatumumab was dosed on Day 1 and Day 8 of Cycle 1, and on Day 1 of Cycles 2 and 3 (initial dose 300 mg, n=21; or 1000 mg, n=40; all subsequent doses 1000 mg). The ORR in the 59 evaluable subjects was 61% with CR in 37%.

Efficacy in rheumatoid arthritis

As of 21 December 2011, efficacy results are available from 3 studies in subjects with RA: Study Hx-CD20-403/OFA112657 Part A and Part B clinical study reports (completed Sept 2008) and follow-up period addenda (completed Dec 2010 and Jan 2011, respectively); Study GEN410/OFA110635 (two interim clinical study reports for the double-blind and open-label periods, completed June 2010 and Dec 2011, respectively); Study GEN411/OFA110634 (one interim clinical study report for the double-blind period, completed August 2011).

In Study Hx-CD20-403 Part A and B, all of the doses tested (300 mg, 700 mg and 1000 mg) resulted in profound B-cell depletion and B-cell levels below normal range or baseline were sustained for approximately 20-34 months. For the primary endpoint analysis (ACR20 response at 24 weeks) in Part B, all doses of ofatumumab were significantly better than placebo, with an ACR20 response being achieved by 40% ($p < 0.001$), 49% ($p < 0.001$), and 44% ($p < 0.001$) of subjects in the 300 mg ($n=58$), 700 mg ($n=57$), and 1000 mg ($n=54$) ofatumumab groups, respectively, compared with 11% in the placebo group ($n=55$). For the 700 mg and 1000 mg groups, significantly better improvements in ACR20 and ACR50 response rates were maintained out to 48 weeks compared with placebo. Subgroup analyses for the subjects on background MTX ($n=174$) showed slightly higher response rates in this subject group.

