Study GEN414/OMS115102 has completed both the 48-week (with 24 week cross-over), double-blind, placebo controlled treatment phase and the individualized follow-up phase. In the Week 0 to 24 period the majority of subjects' CD19+ and CD20+ levels were suppressed to zero; recovery started for the 100 mg and 300 mg active/placebo groups after approximately 12 and 20 weeks, respectively. In the 700 mg active/placebo group, all but one subject had a persistent and complete CD19+ suppression at Week 24. In the Week 24 to 48 period the majority of the subjects' CD19+ and CD20+ levels were suppressed to zero (mm³) within one week in subjects who received active treatment after the treatment cross-over phase. Recovery started for the subjects in the 100 mg placebo/active group after approximately 16 weeks (from these subjects' first infusion). In the 300 mg and 700 mg placebo/active groups, all subjects but one (700 mg) had persistent and complete CD19+ suppression at Week 48. Review of the raw summary statistics highlight the minimal amount of observed new MRI lesion activity following administration of IV ofatumumab in both the Week 0-24 and Week 24-48 treatment periods. Statistical analyses supported the observations from the raw data, showing statistically significant benefits in favour of ofatumumab; caution is needed in the interpretation of the analyses in this small dataset due to the extreme skew in the dataset collected and the assumptions made in the analyses. The observations were consistent in the majority of the exploratory endpoints (cumulative number of new T1 Gd-enhancing lesions, cumulative number of total T1 Gd-enhancing lesions and cumulative number of new and/or enlarging T2 lesions). The assessment of relapses did not show statistically significant differences in ofatumumab treatment from placebo. Although this was primarily a safety and tolerability trial, it also aimed to confirm CD20+ depletion and to obtain preliminary evidence of efficacious effect on MRI and clinical endpoints. The data demonstrated that ofatumumab induced a disease activity response and, as expected, ofatumumab caused profound and selective CD20+ reductions. Overall, the efficacy endpoints indicated that ofatumumab is potentially effective in RRMS patients.

Summary of trial rationale

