The use of topical agents for control of chronic GVHD manifestations is part of usual clinical care for affected patients. Common examples include various eye drops and artificial tears for ocular sicca, steroid or other immune suppressive agent mouth rinses for oral involvement, or topical steroid creams for mild cutaneous involvement. Use of these agents for patients on study will not be controlled or directed by this protocol. Rather, use of these agents will be directed by treating clinicians as part of usual clinical care. Use of these agents will be recorded in data capture on each study visit. Use of these non-systemic therapies will not inform study endpoints that include requirement for additional systemic immune suppressive therapies.

iv. Supportive antimicrobial prophylaxis on study

- i. All patients on study must receive antimicrobial prophylaxis per BMT guidelines and standards for the prevention of bacterial, viral, fungal, and pneumocystis infections.

V. STUDY OUTCOMES/ANALYSIS ENDPOINTS

1. Safety

a. Definition of DLT for phase I component:

- i. In the phase I study, dose escalation will proceed as previously described. The dose limiting toxicity (DLT) will be defined using CTCAE version 4.0 as the following:
 - Events occurring within 46 days of the last dose of drug (4 half-lives) that are:
 - a) Grade 4 infusion reactions,
 - b) Grade 4 constitutional symptoms at least possibly due to ofatumumab,
 - c) Grade 3 organ toxicities (neurologic, pulmonary, cardiac, gastrointestinal, genitourinary, hepatic, cutaneous) at least possibly due to ofatumumab,
 - d) Grade 4 neutropenia lasting more than 14 days
- ii. Importantly, known infusional toxicities of ofatumumab are managed appropriately with modification of infusion rate or temporary halting of infusion, as well as with supportive care including IV fluids, anti-histamines, and steroids.
- iii. Specifically, grade 1-3 infusion-associated adverse events defined by CTC version 4.0 are not considered DLT in this trial. The occurrence of grade 4 infusion-associated adverse event is considered DLT.
- iv. According to observed toxicities in the phase I component, the greatest dose tolerated in the dose escalation will be carried forward into the phase II component of the trial as the recommended phase II dose.
- v. Events clearly related to chronic GVHD, relapse of the primary hematological disorder, concurrent medication, or infection will not be included as a DLT.

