 - iv. Adjustment in the dose of existing immune suppressive agents that require dose modification to maintain therapeutic serum drug levels (e.g. tacrolimus, cyclosporine, sirolimus) is not considered a second-line therapy or change in therapy
 - v. New initiation of extra-corporeal photopheresis (ECP) for progressive chronic GVHD manifestations following study intervention of prednisone and ofatumumab is considered second-line therapy.
- f. Discontinuation of all systemic immune suppressive therapies
- i. The incidence of complete discontinuation of all systemic immune suppressive therapies will be determined.
- g. Failure-free survival
- i. This time-to-event outcome will be estimated with the composite event of death from any cause, relapse and addition of secondary immune suppressive agents for progressive chronic GVHD.
- h. Treatment success
- i. This endpoint will be estimated with a composite outcome of complete resolution of all reversible chronic GVHD manifestations, discontinuation of all systemic immune suppressive agents, and freedom from death or primary malignancy relapse after transplant.
- i. Patient-reported outcomes and functional measures
- i. Patients will provide assessment of their functional ability (grip strength, 2 minute walk test), symptom burden (Lee symptom scale), and quality of life using validated instruments recommended by the NIH Consensus Development Project on Chronic GVHD (Lee Chronic GVHD Symptom Scale,⁴¹ HAP functional scale,⁴² QOL instruments SF-36⁴³ and FACT-BMT⁴⁴)
 - ii. These data will be collected at baseline, 3, 6, and 12 months on study
- j. Biologic studies

Peripheral blood samples will be obtained from study patients at baseline, and then 3, 6, and 12 months. From these peripheral blood samples, the following major analyses will be performed: (1) quantification of plasma B cell stimulatory factor (BAFF), (2) quantification of immune globulin levels, and (3) enumeration of total B cells, as well as characterization of B cell subsets by surface phenotype through flow cytometric analysis.

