a. Phase I (those patients in dose levels that are not the MTD to be carried forward into the phase II component)

i. patients will complete 46 days of follow up from last dose of ofatumumab to monitor for DLT

ii. for those not in the MTD cohort, limited data will be collected at 6 and 12 months (clinical response, pharmacodynamics)

b. Phase II (including patients who are carried forward from the phase I component) – patients will complete 24 total months of follow up on study

e. Clarification on duration of follow up and assessments for phase I patients

a. As the MTD will not be known in real-time, patients on any of the phase I dose levels may potentially be those carried forward from the MTD cohort as the recommended phase II dose

b. Accordingly, patients in all dose levels of the phase I trial will need to have all of the above outlined on-study assessments performed until the MTD is defined.

c. Once the MTD is defined, only those patients in the MTD cohort will continue to have all of the ongoing assessments performed

d. Conversely, those in the non-MTD cohorts will complete an abbreviated assessment measure set to include only the chronic GVHD activity assessments/response determination and the biologic studies (B cell

subsets, BAFF levels) at 6 and 12 month time points. These limited assessments for the non-MTD dose level patients will be included to examine the relationship between dose and clinical response, and dose/pharmacodynamic activity.

VI. STATISTICAL ANALYSIS:

Study design and sample size estimation:

In the phase I component, dose escalation procedure is modeled after the data reported for ofatumumab in treatment of rheumatoid arthritis. Here, doses of 300, 700, and 1000mg were delivered on days 0 and 14. As this dose/schedule was well tolerated, led to significant and sustained (up to 48 weeks) depletion of peripheral blood CD19+ B cells, and there was an association between escalating dose and clinical response ([appendix A](#)), this dose/schedule will be adapted to a phase I design in the primary treatment of chronic GVHD.

The study design of the phase I component represents a traditional (3+3) dose escalation design with the following cohorts of ofatumumab in combination with 1mg/kg/day prednisone therapy:

(cohort -1): 100mg days 0 and 14

cohort 1: 300mg days 0 and 14

cohort 2: 700mg days 0 and 14

cohort 3: 1000mg days 0 and 14

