If at any time the subject meets any of the liver chemistry stopping criteria, then proceed as described above

If after 4 weeks of monitoring, ALT<3xULN and bilirubin<2xULN monitor twice monthly until liver chemistries normalize or return to within baseline values

- b. **Pregnancies:** Pregnancies must be reported to Novartis; however are not to be reported as SAEs unless they meet serious criteria.

2. Special safety monitoring requirements on study:

a. **Hepatitis B Screening**

Follow-up monitoring must be included in the study protocol:

- If HBV DNA is negative, subject may be included
- Monitoring during the follow-up period will be performed during routine study visits for a minimum follow-up period of six months after the last dose, as long as the subject remains on study. Monitoring frequency during follow-up should occur at a minimum of every 3 months. Whenever possible, the monitoring should occur as part of the routine follow-up visit
- Prophylactic antiviral therapy, in addition to the monitoring described above, may be initiated at the discretion of the investigator.

HBsAg positive (regardless of other Hepatitis B serologies):

- exclude

HBsAg negative, HBcAb negative, HBsAb positive

- include

HBsAg negative, HBcAb positive (regardless of HBsAb status)

HBV DNA must be performed

- if HBV DNA is positive the subject is excluded

- If HBV DNA is negative, subject may be included but must undergo at least every 2 month HBV DNA PCR testing from the start of treatment during the treatment course.
- Monitoring during the on treatment periods is required at least every 2 months and during follow-up at a minimum of every 2-3 months up to 6 months after the last dose.
- Prophylactic antiviral therapy, in addition to the monitoring described above, may be initiated at the discretion of the investigator.

If the subjects' HBV DNA becomes positive during the study, the investigator should manage the clinical situation as per the standard of care of that institution, and the Novartis medical monitor should be notified. The risks and benefits of continuing ofatumumab or discontinuing ofatumumab should be discussed with the medical monitor before appropriate treatment decisions are made for that individual subject.

b. Progressive Multifocal Leukoencephalopathy (PML)

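### Required HBV DNA testing of core-antibody-positive patients stops six months after the last dose, earlier than the 48 weeks of B-cell depletion the protocol cites; extending it to month 12 is a cheap improvement

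*Combined protocol and SAP*

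**What the plan says.** Exclusion criterion 12 (section III) keeps HBcAb-positive patients eligible if HBV DNA is undetectable. Section VII, Hepatitis B Screening, then requires PCR testing of HBsAg-negative, HBcAb-positive, HBV DNA-negative patients at least every two months on treatment, and monitoring "during follow-up at a minimum of every 2-3 months up to 6 months after the last dose". A general bullet in the same section sets a floor of six months after the last dose, at least every three months, while the patient stays on study. Antiviral prophylaxis against HBV is left to the investigator. The study calendar has no HBV DNA row, although visits run to month 24.

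On duration of B-cell effect:

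- Section VI, Study design and sample size estimation, says that the day 0 and 14 schedule in rheumatoid arthritis "led to significant and sustained (up to 48 weeks) depletion of peripheral blood CD19+ B cells".
- The background on rheumatoid arthritis says of the same study that "B-cell levels below normal range or baseline were sustained for approximately 20-34 months".
- The background on multiple sclerosis says that "recovery started for the 100 mg and 300 mg active/placebo groups after approximately 12 and 20 weeks, respectively", while at 700 mg "all but one subject had a persistent and complete CD19+ suppression at Week 24".

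On other safeguards, section IV.iv states: "All patients on study must receive antimicrobial prophylaxis per BMT guidelines and standards for the prevention of bacterial, viral, fungal, and pneumocystis infections". HBV is not named there. Section VII schedules liver function tests (LFTs) at each study visit. New abnormalities prompt evaluation in patients with normal baseline values; patients with abnormal baseline values are judged by progression from their starting point. The hepatitis panel in the liver follow-up assessments lists surface antigen and core IgM for hepatitis B.

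**The concern.** HBV DNA monitoring is the specific condition on which HBcAb-positive patients are allowed in. Followed to the letter, the plan stops requiring it while its own data for this schedule suggest that B cells may still be depleted. After that, detection rests mainly on LFT changes. In this population that signal is less specific: section III calls abnormal liver tests a common manifestation of chronic GVHD, so a rise caused by HBV could be put down to the disease. At stake is later recognition of a reactivation in a small, identifiable subgroup. Efficacy conclusions are not affected.

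**Working it through.** No figure in the plan needs reproducing. The check puts the two durations on one clock, in days from the first infusion, with one month taken as 30.44 days.

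**Inputs.** Infusions on days 0 and 14 (section IV); required HBV monitoring to six months after the last dose (section VII); CD19+ depletion up to 48 weeks (section VI); visits at months 6, 9 and 12, each with a window of 14 days either side (study calendar).

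**End of required testing.** Reading the last dose as ofatumumab on day 14: 14 + 6 × 30.44 = 14 + 183 = day 197, about week 28. The last visit scheduled inside this limit is month 6 (day 183, window 169 to 197).

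**End of cited depletion.** 48 × 7 = day 336 if the weeks run from the first infusion. Section VI does not say which dose starts the count; from the second dose it would be 14 + 336 = day 350.

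**Stretch without a required HBV DNA test.**

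- From the first infusion: 336 − 197 = 139 days; 139 / 7 = 19.9 weeks.
- From the second infusion: 350 − 197 = 153 days; 153 / 7 = 21.9 weeks.

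The month 9 visit (9 × 30.44 = day 274) falls inside this stretch. The month 12 visit (12 × 30.44 = day 365, earliest permitted day 351) falls after both end points, so tests at months 9 and 12 would span it.

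**Evidence in the other direction.** In multiple sclerosis at 300 mg, recovery began at about 20 weeks: 20 × 7 = day 140, which is 197 − 140 = 57 days before required testing ends. On that pattern there is no gap before recovery starts. At 700 mg, nearly all subjects were still fully suppressed at week 24 (24 × 7 = day 168), 29 days before testing ends; that passage does not say when they recovered. The infusion interval in that study is not given.

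**What else would detect reactivation after day 197.** LFTs continue at each scheduled visit for patients on full follow-up. The panel is tied to stopping thresholds: ALT above 3 times the upper limit with bilirubin above 2 times, ALT above 8 times, or ALT above 5 times for more than two weeks. Its wording is open-ended, so HBV DNA is not ruled out, but it is not required. For phase I patients outside the MTD cohort, section V.4 says that "for those not in the MTD cohort, limited data will be collected at 6 and 12 months". Once the MTD is defined they therefore also lose the month 9 LFT. At most 12 to 18 phase I patients less 6 at the recommended dose, that is 6 to 12, are in this position.

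**The case against.** The strongest reply is that the plan sets two durations and never links them. Nothing in the documents says that HBV reactivation risk follows CD19+ depletion, or that six months is too short. This stands: the link is a clinical inference, though the protocol itself ties HBV testing to ofatumumab dosing.

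Second, the last dose is not defined as ofatumumab, and prednisone is also study therapy. Two-monthly testing over a treatment course fits poorly with two infusions 14 days apart. Ofatumumab is still the likelier reading, but day 197 depends on it. The general bullet's six months is a floor, so longer testing is allowed; it is not required.

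Third, the LFT safeguard is broader than it may look, because patients with abnormal baseline values are covered through progression from baseline. That is correct. It is an indirect signal and need not lead to an HBV DNA test.

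Fourth, 48 weeks is an upper limit. The background says B-cell data were added at weeks 36 and 48 in that study, so the figure may mark the last sampling rather than recovery. This cuts both ways: some patients recover sooner, and others may not have recovered by then.

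A reader might go further and infer a gap of 20 to 34 months. That figure describes levels below normal range or baseline, which is not the same as full depletion. It shows only that some effect lasts longer. Nor can the gap be sized from the prednisone taper: the protocol does not dictate the taper, and its guide gives no step sizes down to 0.5 mg/kg.

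**Conclusion.** The mismatch is real: required HBV DNA testing ends at about day 197, and the plan's own figure for this schedule runs to as late as day 336. That leaves up to about 139 days (20 weeks), or 153 days if the 48 weeks start at the second dose. This rests on three assumptions: that the last dose means ofatumumab on day 14, that the rheumatoid arthritis figure carries over to chronic GVHD, and that depletion matters for reactivation. The multiple sclerosis data at 300 mg suggest that the gap could be nil at a low dose.

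This is a cheap safety improvement and not an error that undermines the trial. A reader might infer that HBcAb-positive patients are left unprotected, or that a known number will be harmed. The documents support neither. LFTs, mandatory general viral prophylaxis and discretionary HBV antivirals remain, and neither a reactivation rate nor a count of HBcAb-positive patients is given. The number affected could be zero.

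**What to change.** In section VII, Hepatitis B Screening, in the bullet for HBsAg-negative, HBcAb-positive, HBV DNA-negative patients, replace the six-month limit on follow-up with HBV DNA testing at least every 3 months through month 12, done at the existing month 9 and 12 visits. For phase I patients outside the MTD cohort, require it at least at the existing month 12 assessment. In the liver chemistry follow-up assessments, add HBV DNA to the hepatitis panel for HBcAb-positive patients.

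The cost is about two extra PCR tests per HBcAb-positive patient, one for a phase I patient outside the MTD cohort, plus one if the liver panel is triggered. No visits are added: blood is already drawn for LFTs at months 9 and 12 on full follow-up, and the month 12 biologic sample covers the reduced schedule. Eligibility, sample size and endpoints are unchanged. For the reduced-schedule patients the interval from day 197 to day 365 is 168 days, longer than the plan's own 2 to 3 months; that is the price of adding no visit.

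Testing at months 18 and 24 triggered by a low month 12 B-cell count is not recommended. The plan sets no threshold, the assay is a correlative one with no stated return to clinicians, and the background reports that active chronic GVHD itself goes with lower CD19+ counts.

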Appendix B – NIH criteria for diagnosis and severity grading of chronic GVHD

	SCORE 0	SCORE 1	SCORE 2	SCORE 3
PERFORMANCE SCORE:  KPS ECOG LPS	 Asymptomatic and fully active (ECOG 0; KPS or LPS 100%)	 Symptomatic, fully ambulatory, restricted only in physically strenuous activity (ECOG 1, KPS or LPS 80-90%)	 Symptomatic, ambulatory, capable of self-care, >50% of waking hours out of bed (ECOG 2, KPS or LPS 60-70%)	 Symptomatic, limited self-care, >50% of waking hours in bed (ECOG 3-4, KPS or LPS <60%)
SKIN Clinical features:  Maculopapular rash  Lichen planus-like features  Papulosquamous lesions or ichthyosis  Hyperpigmentation  Hypopigmentation  Keratosis pilaris  Erythema  Erythroderma  Poikiloderma  Sclerotic features  Pruritus  Hair involvement  Nail involvement % BSA involved 	 No Symptoms	 <18% BSA with disease signs but NO sclerotic features	 19-50% BSA OR involvement with superficial sclerotic features "not hidebound" (able to pinch)	 >50% BSA OR deep sclerotic features "hidebound" (unable to pinch) OR impaired mobility, ulceration or severe pruritus
MOUTH	 No symptoms	 Mild symptoms with disease signs but not limiting oral intake significantly	 Moderate symptoms with disease signs with partial limitation of oral intake	 Severe symptoms with disease signs on examination with major limitation of oral intake
EYES Mean tear test (mm):  >10  6-10  ≤5  Not done	 No symptoms	 Mild dry eye symptoms not affecting ADL (requiring eyedrops ≤ 3 x per day) OR asymptomatic signs of keratoconjunctivitis sicca	 Moderate dry eye symptoms partially affecting ADL (requiring drops > 3 x per day or punctal plugs), WITHOUT vision impairment	 Severe dry eye symptoms significantly affecting ADL (special eyewear to relieve pain) OR unable to work because of ocular symptoms OR loss of vision caused by keratoconjunctivitis sicca
GITRACT	 No symptoms	 Symptoms such as dysphagia, anorexia, nausea, vomiting, abdominal pain or diarrhea without significant weight loss (<5%)	 Symptoms associated with mild to moderate weight loss (5-15%)	 Symptoms associated with significant weight loss >15%, requires nutritional supplement for most calorie needs OR esophageal dilation
LIVER	 Normal LFT	 Elevated Bilirubin, AP*, AST or ALT <2 x ULN	 Bilirubin >3 mg/dl or Bilirubin, enzymes 2-5 x ULN	 Bilirubin or enzymes > 5 x ULN

	SCORE 0	SCORE 1	SCORE 2	SCORE 3
LUNGS†	 No symptoms	 Mild symptoms (shortness of breath after climbing one flight of steps)	 Moderate symptoms (shortness of breath after walking on flat ground)	 Severe symptoms (shortness of breath at rest; requiring O ₂)
FEV1 				
DLCO 	 FEV1 > 80% OR LFS=2	 FEV1 60-79% OR LFS 3-5	 FEV1 40-59% OR LFS 6-9	 FEV1 ≤39% OR LFS 10-12
JOINTS AND FASCIA	 No symptoms	 Mild tightness of arms or legs, normal or mild decreased range of motion (ROM) AND not affecting ADL	 Tightness of arms or legs OR joint contractures, erythema thought due to fasciitis, moderate decrease ROM AND mild to moderate limitation of ADL	 Contractures WITH significant decrease of ROM AND significant limitation of ADL (unable to tie shoes, button shirts, dress self etc.)
GENITAL TRACT	 No symptoms	 Symptomatic with mild signs on exam AND no effect on coitus and minimal discomfort with gynecologic exam	 Symptomatic with moderate signs on exam AND with mild dyspareunia or discomfort with gynecologic exam	 Symptomatic WITH advanced signs (stricture, labial agglutination or severe ulceration) AND severe pain with coitus or inability to insert vaginal speculum

Other indicators, clinical manifestations or complications related to chronic GVHD (check all that apply and assign a score to its severity (0-3) based on its functional impact where applicable (none – 0, mild -1, moderate -2, severe – 3)

Esophageal stricture or web ___ Pericardial Effusion ___ Pleural Effusion(s) ___
 Ascites (serositis) ___ Nephrotic syndrome ___ Peripheral Neuropathy ___
 Myasthenia Gravis ___ Cardiomyopathy ___ Eosinophilia > 500/μl ___
 Polymyositis ___ Cardiac conduction defects ___ Coronary artery involvement ___
 Platelets <100,000/μl ___ Progressive onset ___

OTHERS: Specify: _____

Global assessment score for chronic GVHD

a. Mild chronic GVHD

- i. Involves only 1 or 2 organs or sites (except lung) with no clinically significant functional impairment (maximum score of 1 in all affected organs or sites).

b. Moderate chronic GVHD

- i. Involves at least 1 organ or site with clinically significant but no major disability (maximum score of 2 in any affected organ or site)
- ii. Or, 3 or more organs or sites with no clinically significant functional impairment (maximum score of 1 in all affected organs or sites).

1. A score of 1 involving the lung is also considered moderate chronic GVHD

c. Severe chronic GVHD

- i. Major disability caused by chronic GVHD (score of 3 in any organ or site)
- ii. Lung score of 2 or greater also considered chronic GVHD

